## 12.1. DERIVATIONS

- BMI expressed in kg/m^2:

$$\text{Weight (kg)}/[\text{height (cm)}/100]^2$$

All other derivations are detailed in SEP380-301 Statistical Analysis Plan, and all derivations are done in SEP380-301 ADaM datasets.

## 13. MEDICAL HISTORY

Unless otherwise specified, the medical and surgical history summary tables will include the following columns: PBO-SEP, SEP-SEP, and ALL EXT (all rollovers from SEP380-301).

Medical and surgical history information, including both past and concomitant medical conditions and major surgical history, as collected on the "*Medical History*" CRF form of study SEP380-301, will be coded using MedDRA, Version 22.0, and presented by SOC and PT for the Safety Population by the actual treatment. Data will be sorted by SOC based on the internationally agreed order (see [APPENDIX 4](#)) and by PT in decreasing frequency in the "ALL EXT" column.

## 14. PRIOR AND CONCOMITANT MEDICATIONS

Unless otherwise specified, the concomitant medications summary tables will include the following columns: PBO-SEP, SEP-SEP, and ALL EXT (all rollovers from SEP380-301).

Medications will be coded to Anatomical Therapeutic Chemical (ATC) Levels and Preferred Names according to World Health Organization Drug (WHODRUG) dictionary, Version SEP2021.

Whenever available, the time information should be accounted for in the derivation of prior, concomitant, and post-treatment medications. See [APPENDIX 2](#) for the handling of partial dates for medications.

- Prior medications are medications which started prior to the first dose of OLE study medication.
- Concomitant medications are medications which started at the same time of or after the first dose of OLE study medication and at the same time of or before the last dose of OLE study medication; or started prior to and ended at the same time of or after the first dose of OLE study medication; or started at the same time of or prior to the last dose of OLE study medication and marked as ongoing.
- Post-treatment medications are medications which stopped after the last dose of OLE study medication or ongoing.

Concomitant medication use will be summarized by ATC Level 3 and Preferred Name for the Safety Population by the actual treatment. If ATC Level 3 is missing, then ATC Level 2 will be used. Medications will be sorted by ATC Level 3 alphabetically and by Preferred Name in decreasing frequency in the "ALL EXT" column.

Prior, concomitant, and post-treatment medications will be provided in data listings.

## 15. STUDY MEDICATION EXPOSURE

Unless otherwise specified, the study medication exposure summary tables will include the following columns: PBO-SEP, SEP-SEP, and ALL EXT (all rollovers from SEP380-301).

Exposure to OLE study medication data will be summarized for the Safety Population by the actual treatment group.

The date/time of first dose of OLE study drug and the date/time of last dose of OLE study drug will be respectively derived as the earliest ("Date Dosing Started" & "Time Dosing Started") pair and the latest ("Date Dosing Ended" & "Time Dosing Ended") pair as collected on the "Study Drug Administration / Drug Accountability" CRF form. The start and end dates/times from blister cards with the number of tablets dispensed equal to the (number of tablets returned + number of tablets reported lost) are excluded from the derivation.

Duration of exposure (in days) will be summarized both as a continuous variable for the OLE treatment period and categorically:

- Number and percentage of subjects with OLE study drug exposure  $\geq 1, \geq 14, \geq 30, \geq 60, \geq 90, \geq 120, \geq 150, \geq 180, \geq 210, \geq 240, \geq 270, \geq 300, \geq 330$ , and  $\geq 360$  days;
- Number and percentage of subjects with OLE study drug exposure for 1 - 13, 14 - 29, 30 - 59, 60 - 89, 90 - 119, 120 - 149, 150 - 179, 180 - 209, 210 - 239, 240 - 269, 270 - 299, 300 - 329, 330 - 359, and  $\geq 360$  days.

Total person-years of exposure to OLE study medication will be calculated for each actual treatment sequence and overall for all subjects in the Safety Population.

Mean daily dose and modal daily dose will be calculated for the entire OLE treatment period and summarized.

The number of days that a subject received the CR 200 mg/day dose level, and the CR 400 mg/day dose level during the OLE treatment period will be summarized for the Safety Population both as a continuous variable and categorically:

- Number and percentage of subjects with exposure to a particular dose level for 1 - 13, 14 - 29, 30 - 59, 60 - 89, 90 - 119, 120 - 149, 150 - 179, 180 - 209, 210 - 239, 240 - 269, 270 - 299, 300 - 329, 330 - 359, and  $\geq 360$  days.

Duration of exposure since SEP380-301 first dose (in days) will be summarized as a continuous variable for the Safety Population by the actual treatment group.

### 15.1. DERIVATIONS

Per protocol, Study drug will be provided in one-week blister cards (7 days + 2 extra days) containing 9 or 18 tablets of SEP-4199 CR 200 mg tablets. The 200 mg blister cards will contain 9 tablets; subjects will be instructed to take a column of one tablet per day, according to dosing instructions.

The 400 mg blister cards will contain 18 tablets; subjects will be instructed to take a column of two tablets each day, according to dosing instructions. Each subject will be dispensed two or four 9-day (7 days + 2 extra days) blister cards per scheduled visit, depending on the timing of the next scheduled visit.

- Duration of exposure (days) = date of last dose of OLE study drug – date of first dose of OLE study drug + 1. Interruptions in exposure (i.e., missed doses) and dose changes (if any) are not considered in the calculation of overall exposure.

- Duration of exposure since SEP380-301 first dose (days) = date of last dose of OLE study drug – date of first dose of study drug in SEP380-301 + 1. This calculation is only performed for the subjects whose actual treatment group is SEP-4199 CR 200, or 400 mg/day in SEP380-301. Interruptions in exposure (i.e., missed doses) and dose changes (if any) are not considered in this calculation.
- The number of days that a subject received a specific dose level (the CR 200 mg/day or CR 400 mg/day) of study medication during the OL treatment period is calculated as the cumulative days the subject is expected to take the specific dose level during the OL treatment period.
- Total person-years of exposure is the sum of all durations of exposure in days / 365.25.
- Mean daily dose (mg/day)

$$\frac{\sum \text{Dose per tablet for Visit } j \times (\# \text{ Tablets Dispensed for Visit } j - \# \text{ Tablets Returned for Visit } j - \# \text{ Tablets Lost for Visit } j)}{\text{Duration of Exposure}}$$

If the number of tablets dispensed, returned, and/or lost as collected on the “*Study Drug Administration / Drug Accountability*” CRF form is missing for one or more visits, the mean daily dose will be calculated based on visits with complete drug accountability data available. That is, the numerator of the formula above will only include visits with the number of tablets dispensed, returned, and lost available, and the denominator should be adjusted to exclude dosing periods covered by visits excluded from the calculation (i.e., Duration of Exposure – dosing periods [sum of (EXENDTC – EXSTDTC+1)] covered by visits with missing or incomplete accountability data). If the dose level of a visit is unknown, that visit should be excluded from the calculation as well in both the numerator and the denominator.

- Modal daily dose will be determined as the daily dose that is taken for the most time (in terms of number of days) among all doses taken. If there are ties, the latest modal dose is used for summary. A subject’s modal daily dose may fall in one of the categories below:
  - o CR 200 mg/day
  - o CR 400 mg/day

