10.1.1. Dose Adjustment Criteria

All subjects will initiate treatment with SEP-4199 CR 200 mg/day. The dose may be increased to 400 mg/day at Visit 2E (Week 2/Day 14) or later, based on the Investigator's judgment. However, if clinically indicated, the dose may be increased as early as Day 7 at an unscheduled visit. The decision to increase the dose and dispense additional study drug will be made by the Investigator at a scheduled or unscheduled study visit. A dose decrease can occur at any time for safety or tolerability concerns (minimum dose of 200 mg/day). If a dose decrease is needed between study visits, subjects will return to the clinic for an unscheduled visit for drug dispensation. Temporary interruption of the study drug is allowed at the Investigator's discretion for specific hyperprolactinemia-related AESI (see Section 13.1).

Prior to a dose increase, safety assessments will be completed, including but not limited to evaluation of adverse events, concomitant medications, vital signs, and ECGs. Subjects whose ECG results, based on machine reading, show increase from Baseline in QTcF interval \geq 30 msec or whose QTcF interval is \geq 480 msec at the 200 mg/day dose are not allowed to have their dose increased to 400 mg/day. Subjects with hyperprolactinemia-related AESI are not allowed to have their dose increased to 400 mg/day. IXRS drug dispensing guidelines should be followed for dispensing the drug to subjects. A specific user manual will be provided.

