10.2. Treatment Compliance

Compliance must be monitored closely and evaluated by the Investigator at each visit. Subjects will be instructed to bring all used blister cards and unused study drug with them to each visit. The number of tablets lost, if any, needs to be reported and recorded. Compliance for a study visit period will be assessed by counting the number of returned tablets, calculated by dividing the actual number of doses taken (= number of tablets dispensed – number of tablets returned – number of tablets lost per tablet count) by the number of doses the subject should have taken and multiplying by 100. All subjects will be reminded of the importance of strict compliance with taking study drug.

Subjects who miss more than 25% of scheduled doses or take more than 125% of the scheduled doses will be considered noncompliant. Evidence of noncompliance must be immediately reported to the Clinical Research Associate (CRA) and/or Medical Monitor.

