## 16. STUDY MEDICATION COMPLIANCE

Unless otherwise specified, the study medication compliance tables will include the following columns: PBO-SEP, SEP-SEP, and ALL EXT (all rollovers from SEP380-301).

Compliance to OLE study medication will be presented for the Safety Population, by the actual treatment group.

Percent compliance will be calculated overall for the OLE treatment period. Non-compliance is defined as less than 75% or more than 125% non-missing compliance for the OLE treatment period. Subjects with missing compliance will not be classified as non-compliant. Compliance will be summarized both as a continuous variable and categorically (i.e., number and percentage of subjects with compliance < 75%, 75% - 125%, > 125%, and missing).

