### 16.1. DERIVATIONS

- Overall Compliance (%) to study medication in percentage will be calculated as follows:

$$\frac{\sum (\# \text{ Tablets Dispensed for Visit } j - \# \text{ Tablets Returned for Visit } j - \# \text{ Tablets Lost for Visit } j)}{\# \text{ Tablets should be taken per day} \times \text{Duration of Exposure}} \times 100\%$$

If the number of tablets dispensed, returned, and/or lost as collected on the "Study Drug Administration / Drug Accountability" CRF form is missing for one or more visits, the overall compliance will be calculated based on visits with complete drug accountability data available. That is, the numerator of the formula above will only include visits with the number of tablets dispensed, returned, and lost available, and the denominator should be adjusted to exclude dosing periods covered by visits excluded from the calculation (i.e., change "Duration of Exposure" to be Duration of Exposure – dosing periods [sum of (EXENDTC – EXSTDTC+1)] covered by visits with missing or incomplete accountability data). In addition, among all the visits included in the overall compliance calculation of a subject, the first visit must have dosing start date (EXSTDTC) available and the last visit must have dosing end date (EXENDTC) available.

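### SAP 16.1 counts days of Investigator-ordered interruption as missed doses when it computes overall compliance

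*SAP*

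**What the plan says.** Protocol 10.2 divides the doses taken "by the number of doses the subject should have taken and multiplying by 100". Its limit on the low side is "Subjects who miss more than 25% of scheduled doses".

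SAP 16 reports one percentage per subject for the whole open-label period, both as a continuous variable and in categories: "Non-compliance is defined as less than 75% or more than 125% non-missing compliance for the OLE treatment period". The formula in SAP 16.1 has tablets dispensed minus returned minus lost in the numerator. The denominator is a single tablets-per-day factor multiplied by Duration of Exposure. SAP 15.1 defines that term: "Duration of exposure (days) = date of last dose of OLE study drug – date of first dose of OLE study drug + 1". It continues: "Interruptions in exposure (i.e., missed doses) and dose changes (if any) are not considered in the calculation of overall exposure".

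SAP 16.1 allows one adjustment, for visits with missing or incomplete accountability data, where "the denominator should be adjusted to exclude dosing periods covered by visits excluded from the calculation". It makes none for interruptions.

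The protocol expects interruptions. Section 10.1.1 states: "Temporary interruption of the study drug is allowed at the Investigator's discretion for specific hyperprolactinemia-related AESI". Sections 12.1.3 and 13.1 refer to re-challenge after an interruption. Protocol 12.3 also lists a temporary stop of study drug among the actions that can be recorded for any adverse event.

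**The concern.** On a day when the Investigator has stopped the drug, no dose is due. Under Protocol 10.2 such a day belongs in neither the numerator nor the denominator. Under SAP 16.1 it stays in the denominator whenever dosing later resumes, because it then lies between the first and last dose. SAP 15 drops blister cards from which nothing was taken, but only when deriving the first and last dose dates, so a gap in the middle remains.

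The error runs in one direction. It lowers compliance for subjects whose drug was interrupted and restarted as the protocol permits, and it can label a subject who followed every instruction as non-compliant. SAP 4.7 lists the main departures from the protocol and this is not among them, so a reader of the compliance table would not know that the denominator differs from the protocol's.

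The problem does not depend on a dose change; it arises for a subject on one dose throughout. A related gap sits in the same formula: the single tablets-per-day factor is not defined for a subject who moves between 200 and 400 mg/day.

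**Working it through.** The documents give no compliance figure to reproduce, so the check applies the stated formula to a fully adherent subject.

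**Inputs**
- D: days from first to last dose inclusive (SAP 15.1).
- I: days of ordered interruption, with dosing resumed afterwards. The protocol sets no maximum. I = 14 is an assumption, taken from the two weeks that Protocol 12.1.3 and 13.1 allow for the named events to resolve. I = 7 and I = 21 are shown as a range.
- k: tablets per day, 1 or 2, held constant (Protocol 9.1).
- Lower limit: 75% (SAP 16). Protocol 10.2 gives the same limit, since 1 − 0.25 = 0.75.
- Every prescribed tablet is taken.

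**Formulas**
- SAP 16.1: 100 × k(D − I)/(kD) = 100 × (D − I)/D. The factor k cancels, so the result is the same at either dose.
- Protocol 10.2: 100 × k(D − I)/[k(D − I)] = 100% for every D and I.

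**Results for I = 14**

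| D (days) | SAP 16.1 | Protocol 10.2 | SAP category |
|---|---|---|---|
| 55 | 41/55 = 74.5% | 100% | non-compliant |
| 56 | 42/56 = 75.0% | 100% | compliant |
| 90 | 76/90 = 84.4% | 100% | compliant |
| 140 | 126/140 = 90.0% | 100% | compliant |
| 360 | 346/360 = 96.1% | 100% | compliant |

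**When the category changes.** (D − I)/D < 0.75 is the same as D < 4I. That means D up to 27 for I = 7 (20/27 = 74.1%), up to 55 for I = 14, and up to 83 for I = 21 (62/83 = 74.7%). At D = 360 the interruption would have to exceed 90 days.

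**A path inside the protocol's rules (timing assumed).** Twenty days on drug, 14 off, 7 on re-challenge, then recurrence and discontinuation give D = 41 and 27/41 = 65.9%. The subject is classed non-compliant with no prescribed dose missed.

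**Imperfect adherence.** At 90% adherence on prescribed days and I = 14, the flag applies when 0.9(D − 14)/D < 0.75, that is 0.15D < 12.6, or D < 84. Such a subject is at 90% by the protocol's measure.

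**Amenorrhea.** The protocol requires at least 3 months of missed menses, taken here as 90 days. If these fall wholly in the extension, followed by 14 days off and one further dose, D is at least 90 + 14 + 1 = 105 and compliance at least 91/105 = 86.7%. If they began on Day 1 of the 42-day lead-in, D is at least 48 + 14 + 1 = 63 and compliance at least 49/63 = 77.8%. Neither is flagged at I = 14.

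**The case against.** The strongest reply is that little depends on this.

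- The category changes only for a short exposure with a proportionately long gap. Two weeks is the protocol's limit for resolution of the named events, not a typical length; a 7-day gap needs D of 27 or less.
- An interruption that is never followed by a restart lies after the last dose and does not enter D.
- A 12-month completer with a 14-day gap loses 3.9 points (14/360) and stays in the same category.
- No inference is planned (SAP 7.6), the Safety Population is the only analysis population (SAP 6), and the important protocol deviation categories named in SAP 11 do not include compliance, though that list is open-ended.
- Site monitoring under Protocol 10.2 keeps its own denominator and is unaffected.

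All of this stands and limits the size of the point.

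It can also be said that the tablets-per-day term might be read as zero on interrupted days. The SAP does not say so: it multiplies one factor by the whole duration. In SAP 15.1 the count of days at each dose level rests on what the subject was expected to take, so the right concept was available and was not used in 16.1.

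Finally, Protocol 12.2 describes discontinuation as mandatory for hyperprolactinemia-related adverse events, while 10.1.1, 12.1.3 and 13.1 provide for interruption and re-challenge. If every such event ended in discontinuation, this scenario would not arise from those events. The passages must be reconciled. As written, the protocol permits interruption, so the SAP has to handle it.

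Three stronger readings are tempting and are not supported:
- A reader might double the gap for a second interruption after re-challenge and extend the flag to D < 112. Protocol 12.1.3 and 13.1 require discontinuation when one of the named events recurs on re-challenge, so a second restart would need a different event.
- A reader might expect the table to show non-adherence among subjects with events of special interest. SAP 16 plans columns by treatment group only, and SAP 8.5 rules out subgroup analyses.
- A reader might think only hyperprolactinemia events are affected. Protocol 12.3 makes temporary interruption a recordable action for any adverse event.

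**Conclusion.** The point holds, with limited reach. As written, SAP 16.1 gives a wrong compliance percentage for any subject whose drug was interrupted on instruction and restarted. The understatement for a fully adherent subject is 100 × I/D points: for I = 14, 15.6 points at D = 90 and 3.9 at D = 360. The change to non-compliant requires resumed dosing and D < 4I, which for a 14-day gap means D of 55 days or less. In practice that means early events followed by early discontinuation or study termination.

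The consequence is confined to the descriptive compliance output by treatment group. How many subjects are affected cannot be told from the documents, which give neither the number of interruptions nor the distribution of exposure. SAP 4.4 reports 64 enrolled subjects; if all were dosed, one misclassified subject is 1/64 = 1.6% of the ALL EXT column, and more within PBO-SEP or SEP-SEP. The figures assume perfect adherence on prescribed days, a constant dose and a 14-day gap.

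**What to change.** In SAP 16.1, replace the denominator with the sum of tablets due over the days on which dosing was prescribed. Use the dose level prescribed on each day and exclude documented Investigator-ordered interruption days. This restores the denominator of Protocol 10.2 and also settles the tablets-per-day factor for subjects who change dose. Leave Duration of Exposure in SAP 15.1 as it is for the exposure tables. If the present formula is kept instead, list it in SAP 4.7 as a change from the protocol and footnote the compliance table.

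The cost is one sentence in the SAP and modest programming. Dosing start and end dates and the adverse event action are already collected, but the documents describe no start and stop dates for interruptions and no field separating ordered from self-initiated gaps. A gap within one blister card may therefore need individual review against the dosing dates and the adverse event record, which is feasible with 64 subjects.

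Separately, reconcile Protocol 12.2 with Protocol 10.1.1, 12.1.3 and 13.1 on whether hyperprolactinemia-related events lead to discontinuation or may be handled by interruption. No view is taken here on which rule should apply.

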## 16. STUDY MEDICATION COMPLIANCE

Unless otherwise specified, the study medication compliance tables will include the following columns: PBO-SEP, SEP-SEP, and ALL EXT (all rollovers from SEP380-301).

Compliance to OLE study medication will be presented for the Safety Population, by the actual treatment group.

Percent compliance will be calculated overall for the OLE treatment period. Non-compliance is defined as less than 75% or more than 125% non-missing compliance for the OLE treatment period. Subjects with missing compliance will not be classified as non-compliant. Compliance will be summarized both as a continuous variable and categorically (i.e., number and percentage of subjects with compliance < 75%, 75% - 125%, > 125%, and missing).

### 16.1. DERIVATIONS

- Overall Compliance (%) to study medication in percentage will be calculated as follows:

$$\frac{\sum (\# \text{ Tablets Dispensed for Visit } j - \# \text{ Tablets Returned for Visit } j - \# \text{ Tablets Lost for Visit } j)}{\# \text{ Tablets should be taken per day} \times \text{Duration of Exposure}} \times 100\%$$

If the number of tablets dispensed, returned, and/or lost as collected on the "Study Drug Administration / Drug Accountability" CRF form is missing for one or more visits, the overall compliance will be calculated based on visits with complete drug accountability data available. That is, the numerator of the formula above will only include visits with the number of tablets dispensed, returned, and lost available, and the denominator should be adjusted to exclude dosing periods covered by visits excluded from the calculation (i.e., change "Duration of Exposure" to be Duration of Exposure – dosing periods [sum of (EXENDTC – EXSTDTC+1)] covered by visits with missing or incomplete accountability data). In addition, among all the visits included in the overall compliance calculation of a subject, the first visit must have dosing start date (EXSTDTC) available and the last visit must have dosing end date (EXENDTC) available.

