9. STUDY DRUG MATERIALS AND MANAGEMENT

9.1. Description of Study Drug

SEP-4199 CR will be supplied as 200 mg tablets containing a fixed 85:15 ratio of aramisulpride:esamisulpride.

- For the SEP-4199 CR 200 mg/day dose, study drug will consist of 1 x 200 mg tablet.
- For the SEP-4199 CR 400 mg/day dose, study drug will consist of 2 x 200 mg tablets.

A description of the investigational product is provided in Table 5.

Attribute	Investigational Product
Product name	SEP-4199 CR 200 mg
Dosage form	Tablets
Unit dose	Tablet
Route of administration	Oral
Physical description	Pale orange round film-coated unmarked tablets
Excipients	D-Mannitol, partly pregelatinized starch, partially hydrolyzed polyvinyl alcohol, hypromellose, light anhydrous silicic acid, sodium stearyl fumarate, Macrogol 400, titanium oxide, talc, ferric oxide yellow, red ferric oxide, and carnauba wax

Table 5:Investigational Product

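### The SAP 16.1 compliance formula uses one tablets-per-day value for the whole exposure, so some fully adherent subjects who change dose are classed as non-compliant

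*SAP*

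**What the plan says.** Protocol 9.1 supplies only a 200 mg tablet: one tablet for 200 mg/day and, for the higher dose, two ("For the SEP-4199 CR 400 mg/day dose, study drug will consist of 2 x 200 mg tablets"). Protocol 10.1.1 states that "All subjects will initiate treatment with SEP-4199 CR 200 mg/day". It allows an increase from Visit 2E (as early as Day 7 at an unscheduled visit) and a return to 200 mg/day at any time. Anyone who ever takes 400 mg/day has therefore changed dose at least once.

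SAP 16.1 computes overall compliance as tablets dispensed minus returned minus lost, summed over visits j, divided by "Tablets should be taken per day} \times \text{Duration of Exposure". The numerator is indexed by visit; the denominator is not. Duration of exposure comes from SAP 15.1 as last dose date minus first dose date plus 1, with the remark that "Interruptions in exposure (i.e., missed doses) and dose changes (if any) are not considered in the calculation of overall exposure".

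SAP 16 sets the classification: "Non-compliance is defined as less than 75% or more than 125% non-missing compliance for the OLE treatment period". The table gives compliance as a continuous variable and in the categories below 75%, 75% to 125%, above 125%, and missing.

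**The concern.** A single product of tablets per day and overall duration suits a subject whose dose never changes. In this flexible-dose study the expected daily tablet count can be 1 for part of the exposure and 2 for the rest, and SAP 16.1 does not say which value then applies.

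There are two consequences. Two programmers could choose different values and get different tables from the same data. And for some subjects either choice is wrong: the percentage then reflects how long the subject spent at each dose and not whether the tablets were taken. The error can also hide poor adherence.

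**Working it through.** The documents state no compliance percentage or count, so there is no figure of theirs to reproduce. The check applies the SAP 16.1 formula to subjects who take every tablet.

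**Inputs.** Tablets per day are 1 at 200 mg/day and 2 at 400 mg/day (Protocol 9.1). The limits are 75% and 125% (SAP 16). The full course is 360 days (Visit 14E, Protocol 11.6.14).

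**Formula.** Let d200 and d400 be the days at each dose, D = d200 + d400, and x = d400/D.

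- Tablets taken = d200 + 2·d400 = D(1+x)
- Value 1: compliance = 100·D(1+x)/D = 100(1+x)%
- Value 2: compliance = 100·D(1+x)/(2D) = 50(1+x)%

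Sanity check at a constant dose: 360/360 = 100% with the value 1 and 720/720 = 100% with the value 2, so the formula works when the dose does not change.

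**Where full adherence fails.**

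- Value 1 exceeds 125% when x > 25%.
- Value 2 falls below 75% when x < 50%.
- Both fail when 25% < x < 50%. With D = 360 this means d400 from 91 to 179 days, since 90/360 = 25% and 180/360 = 50% sit exactly on the limits and pass.

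| Days at 200 / 400 mg/day | Tablets taken | Value 1 | Value 2 |
|---|---|---|---|
| 360 / 0 | 360 | 100.0% | 50.0% |
| 270 / 90 | 450 | 125.0% | 62.5% |
| 240 / 120 | 480 | 133.3% | 66.7% |
| 210 / 150 | 510 | 141.7% | 70.8% |
| 180 / 180 | 540 | 150.0% | 75.0% |
| 14 / 346 | 706 | 196.1% | 98.1% |
| 60 / 30 | 120 | 133.3% | 66.7% |
| 14 / 6 | 26 | 130.0% | 65.0% |

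**Short exposure.** The last two rows show that a long course is not needed. After 14 days at 200 mg/day followed by 400 mg/day, both values fail if the last dose falls on Day 19 to 27. After 60 days at 200 mg/day, they fail for Day 81 to 119.

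**Going up and back down.** An increase after Day 14 and a decrease after Day 180 of 360 gives 166 days at 400 mg/day and 526 tablets: 526/360 = 146.1% or 526/720 = 73.1%. Both fail.

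**Choosing the value by modal dose (SAP 15.1).** For x below 50% the modal dose is 200 mg/day, so the value is 1 and the whole 91 to 179 day band still fails.

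**The reverse error.** A subject raised after Day 14 who takes 60% of the expected 706 tablets has used 423.6. With the value 1 this is 423.6/360 = 117.7%, classed as compliant.

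**The case against.** The strongest reply is that SAP 16.1 never says one value per subject. Tablets to be taken per day could be read as following the prescribed dose, in which case adherent subjects score 100%. There is some support for this. Protocol 10.2 assesses each visit period against what the subject should have taken. Dose changes happen at clinic visits, with drug collected and re-dispensed, so each dispensing period has one tablet count. SAP 15.1 also derives days at each dose level.

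That reading has to be brought in from outside the formula. A product with overall duration needs a single number. When accountability data are missing, SAP 16.1 adjusts only the duration and leaves the tablets-per-day term alone. The mean daily dose formula in SAP 15.1 does index its dose term by visit. It also carries a rule that 16.1 omits: "If the dose level of a visit is unknown, that visit should be excluded from the calculation as well".

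A second reply is that ignoring dose changes is correct for a first-to-last-dose duration, and that mean daily dose uses the same duration without trouble. That is right: the fault lies in the tablets-per-day term, not in the definition of duration.

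A third is that the practical effect is small. Compliance defines no analysis set, nothing is tested, and site reporting of non-compliance follows Protocol 10.2. This also stands, and it limits the weight of the point. Subjects who stay on 200 mg/day are classified correctly with the value 1, and those raised early and kept on 400 mg/day with the value 2.

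**Conclusion.** The concern holds: as written, the denominator in SAP 16.1 gives a wrong classification for some fully adherent subjects, and the choice of value for any dose-changer is left open. Those with more than 25% and less than 50% of their days at 400 mg/day are classed non-compliant whichever of 1 or 2 is used. Outside that band the result depends on the value chosen.

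This assumes one value per subject, which is what the formula shows; a programmer who applied the term by period would avoid the error without any instruction to do so. The documents give no titration pattern, so the number affected among the 64 enrolled is unknown. If all 64 are in the Safety Population, each misclassified subject moves the all-subjects percentage by 1/64, about 1.6 points.

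Duration of exposure, days at each dose level, and mean and modal dose do not use this denominator. The point should be corrected before the table is programmed, but it does not threaten the study's main conclusions.

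**What to change.** In SAP 16.1, replace the denominator with the sum over dosing periods j of prescribed tablets per day in period j times days in period j. Apply the existing exclusion for missing accountability data period by period. Drop periods of unknown dose level from numerator and denominator, as SAP 15.1 already does for mean daily dose.

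For a fully adherent subject the denominator becomes d200 + 2·d400, equal to the tablets taken, so every adherent example above scores 100.0%.

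The cost is one formula edit and minor programming. No new data are needed: SAP 15.1 already derives the days at each dose level ("calculated as the cumulative days the subject is expected to take the specific dose level during the OL treatment period"), and dosing start and end dates are already in use in 16.1.

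A minor and separate clarification: Protocol 10.2 obtains compliance by "dividing the actual number of doses taken (= number of tablets dispensed" and so on, mixing doses and tablets without giving the unit of its denominator. Stating both in tablets would be cleaner. A protocol revision needs written sponsor and IRB/IEC approval (Protocol 17.5), however, and the SAP correction does not depend on it.
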